6.2.1 Definition of an Overdose for This Protocol and Reporting to the Sponsor

For this study, an overdose of pembrolizumab will be defined as any dose of 1000 mg or greater (≥ 5 times the indicated dose).

No specific information is available on the treatment of overdose of pembrolizumab. In the event of overdose, the participant should be observed closely for signs of toxicity. Appropriate supportive treatment should be provided if clinically indicated.

In the event that an inadvertent overdose of pembrolizumab occurs during the trial this should be immediately reported to the Sponsor. Any untoward events occurring as a result of the overdose should be reported within 24 hours to the Sponsor as SAE or ECI per the guidance under section 6.2.3.1

6.2.2 Reporting of Pregnancy and Lactation to the Sponsor

Female patients that are pregnant or breastfeeding, or expecting to conceive within the projected duration of the trial, starting with the screening visit through 120 days after the last dose of trial treatment are excluded from participating in the trial. However in the unlikely event that pregnancy or lactation occurs during the course of the patient's participation in the trial the following section describes the required reporting of these events.

Although pregnancy and lactation are not considered adverse events, it is the responsibility of investigators or their designees to report any pregnancy or lactation in a patient (spontaneously reported to them) that occurs during the trial.

Pregnancies and lactations that occur after the consent form is signed but before treatment allocation/randomization must be reported by the investigator if they cause the patient to be excluded from the trial, or are the result of a protocol-specified intervention, including but not limited to washout or discontinuation of usual therapy, diet, placebo treatment or a procedure.

Pregnancies and lactations that occur from the time of treatment allocation/randomization through 120 days following cessation of trial medication or 30 days following cessation of trial treatment if the patient initiates new anticancer therapy, whichever is earlier, must be reported by the investigator. All reported pregnancies must be followed to the completion/termination of the pregnancy. Pregnancy outcomes of spontaneous abortion, missed abortion, benign hydatidiform mole, blighted ovum, fetal death, intrauterine death, miscarriage and stillbirth must be reported as serious events (Important Medical Events). If the pregnancy continues to term, the outcome (health of infant) must also be reported.

Such events must be reported within 24 hours to the Sponsor. The Sponsor will report within 24 hours (working days) to Merck Global Safety.

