- Symptoms of endocrinopathies, including hypophysitis (including hypopituitarism and secondary adrenal insufficiency), thyroid disorders (hypo or hyperthyroidism and thyroiditis), Type 1 diabetes mellitus, rapid heart rate, change in weight, increased sweating, hunger and/or thirst, frequent urination, hair loss, feeling cold, constipation, deeper voice, muscle aches, unusual and persistent headache, dizziness or fainting.
- Symptoms of nephritis or kidney failure e.g. change in amount or color of urine.
- Symptoms of Guillain-Barre syndrome, pancreatitis, myasthenic syndrome, encephalitis, uveitis, sarcoidosis, and myocarditis (some fatal).

- Symptoms of solid organ transplant rejection, and graft versus host disease (GvHD) in patients who had an allogeneic stem cell transplant after treatment with pembrolizumab.
- Symptoms of other organ issues e.g. rash, changes in eyesight, severe or persistent muscle or joint pain, severe muscle weakness, myositis, severe skin reactions, and anemia. Rarely, severe skin reactions have included cases of Stevens-Johnson syndrome (SJS) and toxic epidermal necrolysis (TEN) some with fatal outcome.
- Symptoms of infusion reactions which may be life-threatening e.g. chills, shaking, shortness of breath, wheezing, itching, rash, flushing, dizziness, fever or feelings of passing out.

Patients with the following may be at particular risk:

- Immune system disorders e.g. Crohn's, ulcerative colitis, lupus.
- Organ transplant – solid organ transplant rejection in donor recipients has been reported. Consider the benefit of treatment with pembrolizumab versus the risk of possible organ rejection in the patients.
- Lung or breathing conditions e.g. interstitial lung disease.
- Liver problems e.g. hepatitis.

The effects of pembrolizumab on unborn fetus and possible transmission through breast milk have not been established. Patients on pembrolizumab should not become pregnant or breast-feed. It is recommended that patients should use adequate birth control and abstain from breast-feeding until at least 4 months after dosing with this product.

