| International normalized ratio (INR) OR prothrombin time (PT) Activated partial thromboplastin time (aPTT) | $\leq 1.5 \times \text{ULN}$ unless participant is receiving anticoagulant therapy as long as PT or PTT is within therapeutic range of intended use of anticoagulants |
| 
ALT (SGPT)=alanine aminotransferase (serum glutamic pyruvic transaminase); AST (SGOT)=aspartate aminotransferase (serum glutamic oxaloacetic transaminase); GFR=glomerular filtration rate; ULN=upper limit of normal. ^a Criteria must be met without erythropoietin dependency and without packed red blood cell (pRBC) transfusion within last 2 weeks. ^b Creatinine clearance (CrCl) should be calculated per institutional standard. Note: This table includes eligibility-defining laboratory value requirements for treatment; laboratory value requirements should be adapted according to local regulations and guidelines for the administration of specific chemotherapies.
 | |

7. Female participants of childbearing potential should have a negative serum pregnancy test within 24 hours prior to receiving first dose of trial medication.
8. A female participant is eligible to participate if she is not pregnant (see Section 4.7.2 not breastfeeding, and at least one of the following conditions applies:
- a.) Not a woman of childbearing potential (WOCBP) as defined in Section 4.7.2.
- OR
- b.) A WOCBP who agrees to follow the contraceptive guidance in Section 4.7.2 during the treatment period and for at least 180 days after the last dose of trial treatment.
9. Male participants must agree to use contraception as detailed in Section 4.7.2 of this protocol during the treatment period and for at least 120 days after the last dose of trial treatment and refrain from donating sperm during this period.

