5.0 Trial Schedule

The trial will consist of the following three periods:

Screening (SCN) Period: The screening period will take place only after informed consent is obtained and within the 21 days prior to C1/D1. The screening visit may be counted as the baseline visit if completed within 7 days of initial dosing on C1/D1.

Treatment Period: Patients will be treated at 21 ± 3 day intervals. Patient must begin cycle 1 within 21 days of signing the IRB approved informed consent document and after the screening assessments have been performed and reports have been reviewed to confirm eligibility. The patient will continue on maintenance therapy until there is evidence of clear-cut tumor progression, has treatment ending toxicities, or withdraws from treatment (refer to section 4.8). Table 7 below summarizes the Screen-Treatment Period Schedule.

Post Treatment Period: Patients will return to the investigative site for an End of Treatment (EOT) visit within 5 days after the last dose of trial treatment or before the initiation of a new anti-cancer treatment, whichever comes first (refer to Section 6.1.7.3). An additional mandatory Safety Follow-up visit should be conducted approximately 30 days after the last dose of trial treatment and before initiation of a new anti-cancer treatment, whichever comes first (6.1.7.4). WOCBP will be required to have a pregnancy test at this visit.

After the 30 day-FU visit, patients will then move into the Survival Phase and be contacted by telephone every 90 days thereafter until death, withdrawal of consent, or the end of the trial, whichever occurs first. The protocol approved contraceptive guidance (Section 4.7.2) must be followed for at least 120 days (for males) and 180 days (for WOCBP) after the last dose of trial treatment. Table 8 below summarizes the Post Treatment Period Schedule.

Footnotes for Table 7. Screen – Trial Treatment Period Schedule

- a. Written IRB-approved informed consent must be obtained prior to any screening assessments being performed.
- b. Documented medical history to include, demographics, concurrent baseline conditions (using NCI-CTCAE V4. Appendix 3), prior cancer treatment and surgeries.

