d. Tumor assessments will be conducted using CT or MRI at trial discontinuation or disease progression, whichever is later. All sites of disease must be followed using the same baseline assessment method.

e. CA19-9 assessments will be taken at baseline and approximately every 3 weeks during the trial treatment period and at the end of treatment visit. All CA19-9 assessments are to be assayed by the same laboratory for each patient. The Investigator is encouraged to obtain radiological assessments and CA19-9 values earlier if there is a strong clinical suspicion of disease progression, in order to confirm or refute the clinical impression.

f. Site to provide patient with Fecal Swab sample collection kit and instructions to collect sample at home within the 72 hours prior to the scheduled 30-day follow-up visit. Patient will return fecal sample to clinic during the scheduled visit, or make

arrangements to drop sample off within 72 hours of collection.

g. Adequate contraception as defined by the protocol should be used throughout the trial and for at least 120 days for males w/WOCBP sexual partner and 180 days for WOCBP from the last dose of trial treatment. Refer to Section 4.7.2. for complete details.

h. Site to confirm contact information for patient and a designated family member and remind patient of FU telephone contact that will be conducted every 90 days for survival status

i. During the Survival Follow-up Phase the patient should be contacted by telephone 90 ± 5 days from EOT and every 90 ± 15 days after that until death, withdrawal of consent, or the end of the trial, whichever occurs first.

j. For only those patients that consent to the optional tissue collection. (Refer to 6.1.2.8).

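### Mandatory pregnancy reporting stops at 120 days (30 if new anticancer therapy starts), although women must use contraception for at least 180 days after the last dose

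*Protocol*

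**What the plan says.** **Contraception.** Inclusion criterion 8b (Protocol Section 4.1.1, repeated in the synopsis) asks a woman of childbearing potential to follow the contraceptive guidance "during the treatment period and for at least 180 days after the last dose of trial treatment". Section 5.0 says that the guidance "must be followed for at least 120 days (for males) and 180 days (for WOCBP) after the last dose of trial treatment". Footnote g of Table 8 repeats it: "for at least 120 days for males w/WOCBP sexual partner and 180 days for WOCBP from the last dose of trial treatment". Section 4.7.2 refers to Section 5.0 for the period. These places agree with each other.

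**Exclusion wording in Section 6.2.2.** Women who are pregnant, breastfeeding or expecting to conceive in a period "starting with the screening visit through 120 days after the last dose of trial treatment are excluded from participating in the trial".

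**Mandatory reporting in Section 6.2.2.** The investigator has to report pregnancies and lactations in a window that opens at randomization and runs "through 120 days following cessation of trial medication or 30 days following cessation of trial treatment if the patient initiates new anticancer therapy". Of these two limits, the one reached first governs.

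**General duty in Section 6.2.2.** Investigators are also responsible "to report any pregnancy or lactation in a patient (spontaneously reported to them) that occurs during the trial". No day limit is attached to this sentence.

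**The concern.** Section 6.2.2 uses one number, 120 days, where the rest of the protocol uses 180 days for women. The 120-day figure matches the contraception period for men, yet the exclusion sentence that contains it is expressly about female patients. The reporting limit can also fall to 30 days.

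Section 4.7.2 says that either drug may harm a fetus. If an investigator applies the explicit limit in Section 6.2.2, a pregnancy that begins while the woman is still under the protocol's contraception requirement may go unreported. The duty to follow a pregnancy to its end attaches to reported pregnancies, so that follow-up would be lost as well.

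**Working it through.** The plan states no figure for the gap, so there is none to reproduce. The check sets the windows side by side. Days are counted from the end of trial treatment, taking the last dose and cessation of treatment as the same day.

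**Inputs**
- Contraception period for women: C = 180 days (Section 4.1.1 criterion 8b, Section 5.0, Table 8 footnote g).
- Reporting limit, no new anticancer therapy: R1 = 120 days (Section 6.2.2).
- Reporting limit, new anticancer therapy started: R2 = 30 days (Section 6.2.2), with the earlier limit governing.
- Contraception period for men: 120 days (Section 5.0, Table 8 footnote g).

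**Step 1, no new therapy.** C − R1 = 180 − 120 = 60 days, that is days 121 to 180.

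**Step 2, new therapy started.** The earlier limit is min(120, 30) = 30. C − R2 = 180 − 30 = 150 days, that is days 31 to 180. This is a maximum. The clause does not say what happens when new therapy begins after day 30. If reporting is read as ending only when new therapy begins, on a day s between 30 and 120, the gap is 180 − s. For example, s = 100 gives 180 − 100 = 80 days. The gap therefore lies between 60 and 150 days.

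**Step 3, men.** Without new therapy, 120 − 120 = 0, so there is no mismatch. If the 30-day clause is applied to partner pregnancies, 120 − 30 = 90 days.

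**Step 4, does other text close the gap for women?**
- The general duty in Section 6.2.2 depends on a spontaneous report and on what counts as during the trial. A specific limit follows it in the same section, and a reader could reasonably apply that limit instead.
- The expedited-reporting page at the front of the protocol refers back to Section 6.2.2 for pregnancy and sets no longer window.
- Section 4.7.3 deals with a patient who becomes pregnant while on treatment.
- Section 6.2.3.1 requires serious events judged related to pembrolizumab to be reported at any time. Section 6.2.2 says that pregnancy is not itself an adverse event, so this route catches at most a bad outcome attributed to that drug.
- The last scheduled pregnancy test is at 30 days (Section 4.7.2, Table 8).

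None of these replaces a defined reporting window.

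**Step 5, is the 30-day case remote?** The synopsis expects 92% of patients to progress by 6 months without maintenance. Confirmed progression ends participation in treatment (Section 4.8), and Section 4.5.2 prohibits no therapy in survival follow-up. The documents do not say how many patients will start new therapy, so the share affected cannot be calculated.

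**The case against.** The best defence is that the two periods serve different purposes. A contraception period can be precautionary, and nothing in the documents says that fetal risk lasts 180 days or that the reporting window must be equally long. That is fair, and the point here does not assume either. But the protocol gives no reason for the difference.

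Four stronger readings are tempting and should be set aside.

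- A reader might infer that a pregnancy after day 120 needs no report at all. The general duty in Section 6.2.2 has no day limit. Table 8 also schedules a contraception review at each 90-day contact, so a late pregnancy may well come to light and be reported. This narrows the gap without closing it.
- A reader might start the 30-day clock when new therapy begins. The clause counts from cessation of trial treatment.
- A reader might see Section 1.4 as a further contradiction, since it says that patients "should use adequate birth control and abstain from breast-feeding until at least 4 months after dosing with this product". This is background text on pembrolizumab, and a 180-day period satisfies a minimum of 4 months.
- A reader might infer that women planning to conceive between days 121 and 180 could be enrolled. Criterion 8b already requires a commitment to contraception for at least 180 days, so the 120-day exclusion wording has little practical effect on eligibility.

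It is also true that the trial has 24 patients and that Section 6.2.2 itself regards pregnancy as unlikely.

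**Conclusion.** The mismatch is real and sits in one place: Section 6.2.2 differs from a contraception requirement that is otherwise stated consistently. For women, at least 60 of the 180 days fall outside the explicit reporting rule, and up to 150 if new anticancer therapy is started. The 150 is a conditional maximum. The general duty and the related-serious-event rule might still catch a case, but they depend on a spontaneous report or on a causality judgement.

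Few cases are likely, and the documents give no count of women of childbearing potential. The consequence is limited to the completeness of safety reporting. The primary endpoint, power and every planned analysis are untouched. It is worth correcting because the subject is fetal exposure and the correction is simple, not because it threatens the trial's conclusions.

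**What to change.** Reconcile Section 6.2.2 with Section 4.1.1, Section 5.0 and Table 8, so that the exclusion wording and the pregnancy and lactation reporting window for women agree with the contraception window. State explicitly whether starting new anticancer therapy shortens pregnancy reporting and, if so, how the limit works when that therapy begins after day 30. The sponsor decides the window; this review does not propose one. Section 1.4 need not change on this account.

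The cost is a wording amendment. No visit or test is added, because contraception use is already reviewed at each 90-day contact, and the extra reporting burden is negligible.

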6.2.3 Immediate Reporting of Adverse Events to the Sponsor and to Merck

6.2.3.1 *Serious Adverse Events*

A serious adverse event is any adverse event occurring at any dose or during any use of pembrolizumab and/or paricalcitol that results in any of the following:

- Death;
- A life threatening adverse drug experience;
- Persistent or significant disability/incapacity;
- Inpatient hospitalization or prolongation of an existing hospitalization;
- Congenital anomaly/birth defect;

Important medical events that may not result in death, be life-threatening, or require hospitalization may be considered a serious drug adverse experience when, based upon

appropriate medical judgment, they may jeopardize the patient and may require medical or surgical intervention to prevent one of the outcomes listed in this definition.

Note: In addition to the above criteria, adverse events meeting either of the below criteria, although not serious per ICH definition, are reportable to the Sponsor and Merck in the same timeframe as SAEs to meet certain local requirements. Therefore, these events are considered serious by Merck for collection purposes.

- Is a new cancer (that is not a condition of the trial);
- Is associated with an overdose.

Refer to Section 6.2.4 for additional details regarding each of the above criteria.

For the time period beginning when the consent form is signed until treatment allocation/randomization, any serious adverse event, or follow up to a serious adverse event, including death due to any cause other than progression of the cancer under study (reference Section 6.2.3.3 for additional details) that occurs to any patient must be reported within 24 hours to the Sponsor. The Sponsor will report within 24 hours (working days) to Merck Global Safety if it causes the patient to be excluded from the trial, or is the result of a protocol-specified intervention, including but not limited to washout or discontinuation of usual therapy, diet, placebo treatment or a procedure.

For the time period beginning at treatment allocation/randomization through 90 days following cessation of treatment, or 30 days following cessation of treatment if the patient initiates new anticancer therapy, whichever is earlier, any serious adverse event, or follow up to a serious adverse event, including death due to any cause other than progression of the cancer under study (reference Section 6.2.3.3 for additional details), whether or not related to the trial treatment, must be reported within 24 hours to the Sponsor. The Sponsor will report within 24 hours (working days) to Merck Global Safety.

Additionally, any serious adverse event, considered by an investigator who is a qualified physician to be related to pembrolizumab that is brought to the attention of the investigator at any time following consent through the end of the specified safety follow-up period specified in the paragraph above, or at any time outside of the time period specified in the previous paragraph also must be reported immediately to the Sponsor. The Sponsor will then report to Merck Global Safety.

All patients with serious adverse events must be followed up for outcome.

